1.8.5 QUALITY CONTROL AND ASSURANCE

Pre-testing of the questionnaires was done on non-study participants and changes made to the questions where necessary before final data collection.

Translation of the consent form into Luganda, the main local language used in Mulago was done prior to the start of data collection.

Research assistants were trained on how to obtain informed consent, patient approach and proper data collection before data collection commenced.

All questionnaires were safely stored to enable revisiting them when necessary.

1.9 ETHICAL CONSIDERATIONS

Ethical approval was sought from the School of Medicine Research and Ethics Committee (SOMREC).

Permission was sought from the Mulago Hospital Ethics committee.

Informed consent was sought from the study participants.

Confidentiality was observed throughout the study.

DATA COLLECTION TOOL

3.5 Pulse....../min.

INCIDENCE OF AND FACTORS ASSOCIATED WITH POST-OPERATIVE NAUSEA AND VOMITING AMONG PATIENTS UNDERGOING REGIONAL ANAESTHESIA

QUESTIONNARE 1 (to be completed by the principal investigator or research assistants) Study Number: Patient's name: **Pre-operative assessment** 1. Case details (state) 1.1 Diagnosis.... 1.2 Procedure..... 2. Urgency of Surgery (Tick one) 2.1 Elective 2.2 Emergency 3. Patient details (preoperative assessment as recorded) 18-30 31-50 3.1 Age (years) 3.2 Sex M 3.3 Weight.....kg. 3.4 ASA classification

3.6 BP.....

4. Patient experience		
4.1 Have you had nausea or vomiting before?		
1=Yes		
4.2 How would you describe the experience?		
1=Very unfavorable 2=Unfavorable		3=Neutral
5 Risk factors for post-operative nausea and vomi	iting	
5.1 Does the patient have any of the following? (Tie	ck appropriately)	
(Multiple choices apply)	1=Yes	2= No
Female		
History of PONV		
History of motion sickness		
Alcohol use		
Smoker		
5.2 Time since the last feed (tick appropriately)		
2hrs 4hrs 6hrs	8hrs [>8hrs
5.3 Type of feeds (tick)		
Solids semi-solids	liquids	

Study Number: Patient's name: 1. Anaesthesia provider (Tick) 1.2 AO 1.3 SHO 1.1 AO student trainee 1.4Anaesthesiologist 2. Length of the operation 2.1 Time surgery i) started...... ii) ended (state in 24hour clock) 2.2 Duration of anaesthesia 30 min L 30-60min 60-120min >120min 2.3 Duration of surgery 30 min ____ 30-60min 60-120min >120min 3. Conduct of anaesthesia and surgery 3.1. Type of Surgery Emergency Elective 3.2. Anaesthetic technique (state)

1=Yes

2=No

QUESTIONNAIRE 2

Sedation used

3.3. Number of attempts at the block(tick) 1	2	>2
3.4.Drugs used during anaesthesia(tick)		
o. i.Di ugo useu during anaestnesia(tiek)	1=Yes	2=No
	1–1 es	2-110
Opioids		
If yes, state which opioid	••••	
Anti-emetics		
If yes, state which anti-emetic		
Sedatives		
If yes, state which sedative		
3.5.Did any of the following happen duri	ng surgery? (Tick aj	opropriately)
	1=Yes	2=No
Retching		
Nausea		
Vomiting		
3.6.Lowest BP recorded(tick)		
SBP <110 <90	<50	
DBP <90 <70	<50	

4. Recovery room

[figure not shown]
5.1 Did any of the following happen during recovery? (Tick appropriately)

	1=Yes	2=No
D . 11		
Retching		
Nausea		
rvausca		
Vomiting		

5. At 24 hours (tick)

5.1 Nausea or vomiting 1= Yes 2=No 5.2 If yes, time to occurrence of PONV from time of surgery.....hours.....min
5.3 Post-operative opioids received 1=Yes 2=No 2=No

6. Pain assessment

If yes, state which opioid

Rating	Pain Level
0	No Pain
1 – 3	Mild Pain (nagging, annoying, interfering little with ADLs)
4 – 6	Moderate Pain (interferes significantly with ADLs)
7 – 10	Severe Pain (disabling; unable to perform ADLs)

RISK FACTORS FOR NAUSEA AND VOMITING SCORING SYSTEM (aPFEL)

Risk Factors	Points
Post-operative Opioids	1
Non Smoker	1
Female Gender	1
History of PONV/Motion Sickness	1
Risk score = sum	0 4

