1.8 DATA MANAGEMENT

1.8.1 DATA COLLECTION

A standardised questionnaire was completed by the study research assistants or the principal investigator during the immediate pre-operative period to assess pre-operative risk of post-operative nausea and vomiting. The information collected included patient demographics, past medical history, information on fasting and co-morbidities. A second questionnaire was used to assess the perioperative conduct of anaesthesia and any events occurring within this period. It contained the follow up information as well.

Patients were followed up once at 24 hours to assess for post-operative nausea and vomiting.

1.8.2 INDEPENDENT VARIABLES:

Socio demographic data such as age and sex, the diagnosis and type of procedure, ASA classification, history of PONV or motion sickness, non-smokers, peri-operative opioid use, period of pre-operative fasting, PONV prophylaxis use, duration of anaesthesia and surgery were studied.

1.8.3 DEPENDENT VARIABLE:

Post-operative nausea and vomiting measured by any retching, nausea or vomiting within 24 hours following surgery under regional anaesthesia.

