1.8.4 DATA ANALYSIS AND SAFETY

Completeness and accuracy of data was checked daily and organised by the principal investigator before storage. Data was double entered into the computer using EPI data version 3.1, and then subsequently exported to STATA version 14.0 for analysis.

Analysis was done using STATA with the help of a statistician. Both raw data and the analysed form were kept both electronically and hardcopy for further reference.

All questionnaires were stored in a secure, waterproof place to enable confidentiality and were only available to the principal investigator.

Participant characteristics were expressed as categorical and/or continuous variables.

Continuous variables were expressed as means and standard deviations while categorical data was expressed as frequencies with their respective proportions. Data presentation is in tabular and graphic forms.

Cumulative incidence was assessed as the proportion of study participants who developed PONV within 24 hours of follow up divided by the total number of study participants enrolled into the study with complete follow up.

At the bivariate level, each variable was compared with the outcome variable using cross tabulation and the logistic analysis. Variables that had p-value less than 0.200 at bivariate analysis were considered for multivariate analysis using logistic regression and variables were considered significant if the p-value <0.05.

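### Could post-operative opioids recorded without a time at 24 hours be counted as a factor for PONV that came before them?

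*Protocol*

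**What the plan says.** Section 1.8.2 of the Protocol gives the independent variables; its list closes with "peri-operative opioid use, period of pre-operative fasting, PONV prophylaxis use, duration of anaesthesia and surgery were studied". It names no form item, time window or coding rule for the opioid variable.

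Questionnaire 2 has two opioid entries:

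- Item 3.4, headed "3.4.Drugs used during anaesthesia(tick", asks yes/no for opioids and which one.
- Item 5.3, "5.3 Post-operative opioids received", stands in the block completed at 24 hours and also asks yes/no and which one.

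In the same block, item 5.2 asks for "time to occurrence of PONV from time of surgery" in hours and minutes. Section 1.8.1 describes a single contact: "Patients were followed up once at 24 hours to assess for post-operative nausea and vomiting". The part of the form headed "4. Recovery room" is not legible in the available copy.

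Under section 1.8.4, "each variable was compared with the outcome variable using cross tabulation and the logistic analysis". The next step is a screen: "Variables that had p-value less than 0.200 at bivariate analysis were considered for multivariate analysis using logistic regression".

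**The concern.** The form times the outcome but, as far as it can be read, not the post-operative opioid. A patient who vomits at hour 2 and first receives an opioid at hour 10 would answer yes to item 5.3 and enter the cross tabulation as an exposed case. If prescribers hold opioids back once a patient is sick, cases lose exposure and opioids look protective. If cases tend to receive more opioids later, opioids look harmful. Either way a consequence of PONV could be reported as a factor for it.

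Factors associated with PONV are a main aim of the study, and post-operative opioids are one of the four items on the risk score printed with the form. A time that was never collected also cannot be restored by later analysis text, so the matter seemed to go beyond a missing definition.

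**Working it through.** **Which item is meant.** The Protocol points both ways.

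| Place | Points to |
|---|---|
| Section 1.7, data gathered: mentions intra-operative medication, not post-operative opioids | item 3.4 |
| Apfel table on the form: one point for post-operative opioids | item 5.3 |
| Section 1.8.2: peri-operative | 3.4, 5.3, or either |

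Under the last reading, the ordering question touches only patients with no intra-operative opioid.

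**Inputs from the Protocol.** Section 1.5 gives an incidence of 31.4% and, for objective 1, 1.96² × 0.314 × 0.686 / 0.05² = 330.998, so 331. With the 10% allowance, 331 × 1.10 = 364.1, stated as 364. Both figures reproduce, and neither depends on the opioid definition. With 331 complete follow-ups, the expected number of cases is 331 × 0.314 ≈ 104.

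**Assumptions, not in the Protocol.** There is no true opioid effect. A share e = 0.5 is exposed. Then:

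- w = share of not-yet-given opioids withheld after PONV;
- x = share of otherwise unexposed cases given an opioid later;
- f = share of would-be-exposed cases whose PONV precedes the first dose. It comes from a PONV hazard proportional to exp(−t/τ), calibrated to 31.4% over 24 h, with the first dose uniform over a stated interval.

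**Formula.** Exposure among non-cases is e. Among cases it is e(1 − wf) under withholding, or e + (1 − e)x under later extra use. At e = 0.5:

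- withholding: OR = (1 − wf)/(1 + wf)
- later extra use: OR = (1 + x)/(1 − x)

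**No reaction** (w = x = 0): OR = 1.00. A two-sided Wald test gives p<0.05 in 5% of studies, and 20% pass the 0.200 screen. These are the nominal rates.

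**Withholding, w = 0.3, τ = 6 h:**

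| First dose | f | OR | p<0.05 | passes 0.200 |
|---|---|---|---|---|
| 0-2 h | 0.176 | 0.90 | 7% | 24% |
| 0-4 h | 0.310 | 0.83 | 12% | 33% |
| 0-6 h | 0.413 | 0.78 | 18% | 42% |
| 1-12 h | 0.659 | 0.67 | 39% | 65% |

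For example, the 1-12 h row has wf = 0.3 × 0.659 = 0.198, and 0.802/1.198 = 0.67.

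**Later extra use, x = 0.2:** OR = 1.2/0.8 = 1.50. The standard error of the log OR is √(1/62.4 + 1/41.6 + 2/113.5) = 0.240, so the expected z is 0.405/0.240 = 1.69. That gives p<0.05 in 39% of studies, and 66% pass the screen.

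**Small reactions.** With w = 0.1 and τ = 6 h, the OR is 0.97 to 0.88 and p<0.05 occurs in about 5-9% of studies. With x = 0.05, OR = 1.05/0.95 = 1.11 and the rate is about 7%.

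**Full range.** Withholding of 10-50% with τ of 3-12 h gives OR 0.98 to 0.41. Extra use of 5-30% gives 1.11 to 1.86. The exposed share matters too: at x = 0.2, the OR is 2.00 with 25% exposed and 1.33 with 75% exposed. All rejection rates are for the unadjusted test; section 1.8.4 goes on to a multivariable model.

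**The case for a change.** The strongest case for a change is that the missing opioid time belongs to data collection, not to analysis. A statistical analysis plan can say which item is used, but it cannot put an untimed yes/no in order against a timed event. The proposed remedy looks cheap: take item 3.4 as the model's opioid factor, since it precedes the post-operative window, and report item 5.3 descriptively.

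Part of this stands. On the visible form, item 5.3 does not show whether the opioid came before PONV, and an odds ratio from it should not be read as the effect of an earlier exposure. Even with no reaction to PONV, a true effect of earlier opioids would be diluted by doses given afterwards.

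The rest does not carry a change.

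- The recovery-room block is not legible and the text around item 5.3 is scrambled, so a further opioid entry cannot be ruled out.
- Substituting item 3.4 answers a different question and leaves out a factor that the form's own score counts. Statisticians would differ on whether that is an improvement.
- A time-dependent analysis would need first-dose times from records that the Protocol does not show to exist. It would also need a clear time origin, and item 5.2 says only that PONV is timed from surgery.
- Recruitment ran from August 2018 to January 2019 and the Protocol is written in the past tense, so the form itself cannot be altered.

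**Conclusion.** No change to the plan is called for. What the Protocol leaves open is the link between one listed variable and two form items, a detail commonly settled in the analysis plan; nothing it states on this point is wrong or contradictory.

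A false association needs two things that the Protocol does not establish: that item 5.3, alone or combined with 3.4, supplies the factor, and that prescribing reacts to PONV. Without the second, the odds ratio under no true effect is 1.00 and error rates are nominal. With it, the direction is not fixed, and the size runs from negligible to substantial (0.41 to 1.86 at 50% exposed) according to assumed reaction rates and dose timing. Only the 31.4% and the 331 come from the document.

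The study reports factors associated with PONV, and a 24-hour association is what item 5.3 can give. A sensible analyst would show items 3.4 and 5.3 as separate factors, note that the order of post-operative opioids and PONV is unknown, and perhaps add a model without 5.3. That is a matter of reporting and does not require item 5.3 to leave the main model.
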